# 15.1 Definitions of Adverse Events

# 15.1.1 Adverse Event (AE)

An **adverse event** is defined as untoward medical occurrence associated with the use of a medical intervention in humans, whether or not considered related to the medical intervention. An adverse event can be **ANY** unfavorable and unintended sign (e.g. an abnormal laboratory finding), symptom, or disease temporarily associated with the use of a medicinal (investigational) product, whether or not considered related to the medicinal (investigational) product (attribution of 'unrelated', 'unlikely', 'possible', 'probable', or 'definite'). Acute adverse events will be graded according to the NCI Common Toxicity Criteria, Version 4.0.

# 15.1.2 Serious Adverse Event (SAE)

A serious adverse event is any untoward medical occurrence resulting in one or more of the following:

• Results in death or ANY death occurring within 28 days of the last fraction of SBRT (even if it is not felt to be related to the medical intervention)

- Is life-threatening (defined as an event in which the patient was at risk of death at the time of the event; it does not refer to an event which hypothetically might have caused death if it were more severe)
- Requires inpatient hospitalization or prolongation of existing hospitalization NOTE: Hospitalizations that are not considered SAEs are:
  - Hospitalization planned prior to first administration of study treatment
  - Hospitalization for elective treatment of a pre-existing condition unrelated to the study treatment
- Results in persistent or significant disability/incapacity
- Is a congenital anomaly or birth defect
- Is an important medical event (defined as a medical event(s) that may not be immediately life-threatening or result in death or hospitalization but, based upon appropriate medical and scientific judgment, may jeopardize the patient or may require intervention (e.g., medical, surgical) to prevent one of the other serious outcomes listed in the definition above). Examples of such events include, but are not limited to, intensive treatment in an emergency room or at home for allergic bronchospasm; blood dyscrasias or convulsions not resulting in hospitalization; or the development of drug dependency or drug abuse.
- Pregnancy

Pregnancy of a patient during the study or within 30 days after the last fraction of SBRT should be reported via an SAE report. Should pregnancy occur in a female participant during the treatment period, SBRT should be discontinued.

# 15.1.3 Unexpected Adverse Event

An adverse event not mentioned in the informed consent or the specificity or severity of which is not consistent with the informed consent, or is not common within the patient population.

# 15.2 Determining Attribution to the Investigational Agent(s)

**Attribution:** An assessment of the relationship between the AE and the medical intervention. CTCAE does not define an AE as necessarily "caused by a therapeutic intervention". After naming and grading the event, the clinical investigator must assign an attribution to the AE using the following attribution categories:

Relationship	Attribution	Description
Unrelated to	Unrelated	The AE is clearly NO T related
investigational agent/intervention	Unlikely	The AE is doubtfully related
Related to investigational	Possible	The AE may be related
agent/intervention	Probable	The AE is likely related

	Definite	The AE is clearly related
--	----------	---------------------------

# 15.3 Adverse Event (AE) and Serious Adverse Event (SAE) Reporting

Acute adverse events (CTCAEs) will be recorded from the time of first SBRT and for at least 90 days after treatment discontinuation, regardless of whether or not the event(s) are considered related to SBRT. All Acute AEs considered related to SBRT will be followed until resolution, return to baseline, or deemed clinically insignificant, even if this occurs post-trial.

All SAE's should be collected from the first fraction of SBRT until death or the patient enrolls in hospice. SAE's related or possibly related to study treatment or a study procedure should be reported until the patient is off study. Any death occurring within 30 days after the last fraction of SBRT or last study procedure must be reported as an SAE regardless of attribution.

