- Creatinine ≤ institutional upper limit of normal OR creatinine clearance >60 mL/min/1.73 m² for patients with creatinine levels above institutional normal
- Ability to understand and the willingness to sign a written informed consent document.
- Life expectancy > 3 months.
- Radio-opaque markers must be present within the tumor bed. In patients who
  have undergone surgical resection, radio-opaque surgical clips within the tumor
  bed can be used as fiducials. Patients without surgical clips in the tumor bed
  must be able to have fiducials placed endoscopically, laparoscopically, or
  through a CT- or ultrasound-guided technique. If not, the tumor must be
  posterior and adjacent to the aorta, and treatment will only be permitted at the
  discretion of the Principal Investigator.

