#### 7.1.1 Fiducials

Treatment on this protocol requires placement of 1-5 gold (99.9% pure, 1-5 mm length, or visicoils) fiducials for targeting purposes. The fiducials will be used as surrogates for targeting the daily tumor position during treatment. The fiducials will be placed directly into the tumor and/or periphery under endoscopic ultrasound or

CT guidance. When possible, clips or fiducials will also be placed in the proximal duodenum directly adjacent to the pancreatic tumor. Fiducials may be implanted prior to enrollment, as this is an acceptable standard of care procedure for any patient receiving radiotherapy for locally advanced pancreatic or periampullary cancer. Patients who have undergone surgical resection or attempted surgical resection may already have clips or fiducials in the tumor bed, which are acceptable markers for the purposes of this study.

If fiducials are not placed intraoperatively and/or prior to enrollment, placement will be done and is expected to be done on an outpatient basis. In rare occurrences when fiducials/clips cannot be placed, patients may be treated at the discretion of the PI.

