#### 11.4 Analysis Datasets

- Enrolled Population The enrolled population consists of all patients who enroll in the study.
- Efficacy Population The efficacy population comprises all patients who meet
  the eligibility criteria, are registered onto the study, get at least one session of
  Linac-based SBRT, and have at least one follow-up evaluation. This set will be
  used for efficacy analysis.
- Safety Population The safety population comprises all patients who have received at least one session of Linac-based SBRT. This set will be used for safety analysis.

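### Section 15.3 starts AE and SAE collection at the first SBRT fraction, so complications of on-study fiducial placement that begin before it are not clearly captured

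*Combined protocol and SAP*

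**What the plan says.** Section 15.3 sets two starting points, and they coincide. For AEs: "Acute adverse events (CTCAEs) will be recorded from the time of first SBRT and for at least 90 days after treatment discontinuation". For SAEs, all of them "should be collected from the first fraction of SBRT until death or the patient enrolls in hospice". Two further sentences in the section mention procedures. SAEs "related or possibly related to study treatment or a study procedure should be reported until the patient is off study", and "Any death occurring within 30 days after the last fraction of SBRT or last study procedure" must be reported as an SAE whatever its cause. Neither sentence says when the duty begins.

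On fiducials, section 7.1.1 states: "Treatment on this protocol requires placement of 1-5 gold" fiducials. It accepts clips or fiducials that are already in place, allows placement before enrollment as standard of care, and lets the PI treat the rare patient in whom none can be placed. For the rest: "If fiducials are not placed intraoperatively and/or prior to enrollment, placement will be done". The eligibility text in 4.1 says "Radio-opaque markers must be present within the tumor bed", but goes on to admit patients without clips if they are able to have fiducials placed. Placement after enrollment is therefore foreseen.

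The analysis set is defined in 11.4: "The safety population comprises all patients who have received at least one session of Linac-based SBRT".

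**The concern.** The trial's stated focus is safety (11.5). Delivery of SBRT generally depends on an invasive placement step, and for some patients that step takes place while they are already enrolled. If event collection opens only at the first fraction, a serious complication of that step can begin and resolve before anyone is asked to record it.

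A patient harmed badly enough never to start SBRT is also excluded from the safety population, so the safety tables would not show the event even if it had been written down. DSMC review of SAEs (15.3.2) works from what the study team enters in OnCore, so an SAE outside the collection rule may not reach it by that route.

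**Working it through.** The plan states no figure on this point, so the check is mainly a comparison of sections, followed by an illustration of size.

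**Order of events**

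1. Section 7.1 lists fiducial placement among the items completed before SBRT, and the section 9 calendar puts it in the pre-study column.
2. Section 7.1.2 says that simulation should follow placement, subject to PI discretion, and that SBRT must start within 4 weeks (28 days) of simulation.
3. The calendar footnote sets the pre-study window at 45 days before study treatment.
4. Placement can therefore precede the first fraction by several weeks. Both starting points in 15.3 lie after that interval.

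**Search for an earlier start.** No section opens AE or SAE collection at consent, enrollment or placement. The calendar's AE evaluation row has no pre-study entry. Section 12 collects dates and findings of procedures, including fiducial placement, but not as graded and attributed adverse events.

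**Sentences of 15.3 side by side.** Take an enrolled patient who has a serious complication after placement and before SBRT.

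- Under the general SAE sentence, the event precedes the start of collection.
- Under the procedure-related sentence, it is reportable if placement counts as a study procedure and if the duty reaches back before SBRT. The documents settle neither condition.
- Under the death rule, if the patient dies within 30 days of placement and placement was the last study procedure, the death is reportable, although it too precedes the start in the general sentence.
- For AEs that are not serious there is no competing sentence. The start at first SBRT stands alone.

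**Illustration of size.** The only input from the documents is the total enrollment of 38 (11.5). The serious complication rate *p* (1% to 5%) and the number of on-study placements *n* are assumptions. Expected events are *n* × *p*, and the chance of at least one is 1 − (1 − *p*)^*n*.

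| *n* | *p* | Expected events | Chance of at least one |
|---|---|---|---|
| 38 (all) | 1% | 38 × 0.01 = 0.38 | 1 − 0.99^38 = 0.317 |
| 38 (all) | 5% | 38 × 0.05 = 1.9 | 1 − 0.95^38 = 0.858 |
| 19 (half) | 1% | 19 × 0.01 = 0.19 | 1 − 0.99^19 = 0.174 |
| 19 (half) | 5% | 19 × 0.05 = 0.95 | 1 − 0.95^19 = 0.623 |

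In every row, for these to be missed events, each complication must begin before the first fraction and none may be reported under the procedure-related sentence. The rows for 38 are an upper case, because 4.1 and 7.1.1 expect some patients to arrive with clips or fiducials.

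**The case against.** The intervention under test is SBRT. Opening collection at first exposure and defining safety on treated patients is a common and defensible choice. Section 7.1.1 describes placement as acceptable standard of care for patients of this kind, so many would face the same risk outside the trial, and no section calls it a study procedure. This is a fair reason for keeping placement events apart from SBRT toxicity. It is weaker as a reason for not collecting them when placement happens on study because treatment on the protocol requires it.

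A reader might infer that 15.3 contradicts itself outright. The text does not go that far. The procedure-related sentence has an end and no start, so it can be read as a separate duty not tied to the first fraction. The section is ambiguous for SAEs.

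A reader might also infer that all placement complications are lost. Those that begin after the first fraction fall inside the window, and AEs there are recorded regardless of attribution, subject to the grade 3 reporting threshold in section 15.

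Nor would an earlier event necessarily leave no trace. Section 12 records procedure findings and the date and reason for withdrawal. Section 11.8 tabulates discontinuations among all enrolled patients with reasons. Section 14 requires continuous safety review and monthly summaries to the DSMC. Section 15.3.1 sends certain unexpected, research-related problems to the IRB. These routes are real but partial. None of them yields a graded, attributed event, and a recognised procedural complication may not meet the IRB criteria for prompt reporting.

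**Conclusion.** The point holds as a gap in safety reporting of limited scope. It concerns patients whose fiducials are placed after enrollment, and complications that begin before the first fraction. For non-serious AEs in that interval the rule plainly excludes them; for SAEs 15.3 leaves the matter open and its sentences must be reconciled. Patients prevented from starting SBRT are outside the safety population on any reading.

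It would be tempting to conclude that the toxicity estimate is biased. The documents do not support that. The primary endpoint is acute toxicity within 3 months of treatment (3.1, 11.9), and the stopping rule counts treatment-related Grade 4 or 5 events (11.3). Neither depends on events before SBRT.

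No probability follows from the documents alone. The ranges of 32% to 86% (all 38 placed on study) and about 17% to 62% (half) rest entirely on the assumed 1% to 5% rate and the assumed number of placements. They show only that an uncaptured serious event is plausible. The change is worth making because it improves safety reporting at little cost.

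**What to change.** In section 15.3:

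- State that fiducial placement done on study counts as a study procedure.
- Collect SAEs, and AEs of grade 3 or higher, that are related to a study procedure from consent or from the first study procedure after enrollment. Name which of the two applies.
- Give the procedure-related SAE sentence and the death rule that same start, so that they agree with the general SAE sentence.
- Keep the first fraction as the start for SBRT toxicity, so that the primary endpoint and the stopping rule are unchanged.

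In the analysis plan, add a listing of procedure-related events before SBRT for the enrolled population already defined in 11.4, including patients who never start SBRT. Keep it separate from the tables for the safety population.

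The cost is a short edit to 15.3, one listing and a few more event forms. Treatment, endpoints and sample size do not change.

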# 15.3.1 Reporting to the IRB

Unanticipated problems involving risks to subjects or others will be reported **promptly** to the IRB if they:

- unexpected;
- related or possibly related to participation in the research; and
- suggests that the research places subjects or others at a greater risk of harm than was previously known or recognized.

If the serious adverse event does not meet all three (3) criteria listed above, the event does not have to be promptly reported to the Indiana University IRB. However, it should be reported at the time of continuing review.

**Prompt** reporting of unanticipated problems to the IRB is defined as within 5 days from becoming aware of the event.

# 15.3.2 Reporting to the IUSCC Data Safety Monitoring Committee (DSMC)

Regardless of study sponsorship, the study team must enter all initial and follow-up SAE, expedited, and noncompliance reports into OnCore® for review by the DSMC chair and/or coordinator. Expedited reports may include IRB Prompt Report Forms and additional SAE forms as required by the sponsor. When follow-up information is received, a follow-up report should also be created in OnCore®. This DSMC reporting requirement is **in addition to any other** regulatory bodies to be notified (i.e. IRB, FDA, pharmaceutical company, etc.). The DSMC chair and/or coordinator will review all SAE, expedited, and noncompliance reports monthly.

#### 17. APPENDICES

# A1. Appendix I: NCI Common Toxicity Criteria Version 4.0

Due to the size of the latest version of the Common Toxicity Criteria, copies of this appendix are not included with this protocol document.

An electronic copy is available on the CTEP web site, http://ctep.cancer.gov/reporting/ctc.html

# **A2.Appendix II: Performance Status Scales/Scores**

ECOG or Zubrod			Karnofsky	I	ansky
S	Score Activity	So	core Activity	Se	core Activity
	Fully active, able to carry on all predisease	100	Normal, no complaints, no evidence of disease.	100	Fully active, normal.
0	performance without restriction.	90	Able to carry on normal activity; minor signs or symptoms of disease.	90	Minor restrictions in physically strenuous activity.
	Restricted in physically strenuous activity but ambulatory	80	Normal activity with effort some signs or symptoms of disease.		Active, but tires more quickly.
1	and able to carry out work of a light or sedentary nature, e.g., light housework, office work.	70	Cares for self, unable to carry on normal activity or do active work.	70	Both greater restriction of and less time spent in play activity.
2	Ambulatory and capable of all selfcare but unable to carry out any work activities.	60	Requires occasional assistance, but is able to care for most of his/her needs.	60	Up and around, but minimal active play; keeps busy with quieter activities.
	Up and about more than 50% of waking hours.	50	Requires considerable assistance and frequent medical care.	50	Gets dressed, but lies around much of the day; no active play; able to participate in all quiet play and activities.
3	Capable of only limited selfcare, confined to bed or	40	Disabled, requires special care and assistance.	40	Mostly in bed; participates in quiet activities.
3	chair more than 50% of waking hours.	30	Severely disabled, hospitalization indicated. Death not imminent.	30	In bed; needs assistance even for quiet play.
4	Completely disabled. Cannot carry on any	20	Very sick, hospitalization indicated. Death not imminent.	20	Often sleeping; play entirely limited to very passive activities.
4	selfcare. Totally confined to bed or chair.	10	Moribund, fatal processes progressing rapidly.	10	No play; does not get out of bed.

# A3.Appendix III: DSMC Check Sheet

[figure not shown]
#### Meeting Minutes Form for DSMC

send to [contact] or file in binder

Meeting Date:			
Team/Program: (include meeting sign in sheet)			
Protocol & Status (open/closed to accrual) (one protocol per sheet)			
PI:			
	Υ	N	
Weekly and Monthly meetings should include discussion on data, dose levels, accrual numbers, deviation summaries and SAE reports (per IUSCC DSMP).			
Has accrual been reviewed and entered into Oncore?			
Have all SAE's been entered into Oncore?			
Is there documentation for study discontinuation?			
Have all deviations been entered into OnCore?			
Have study deviation summaries been reviewed by the team (CTO continue to keep deviation logs signed by PI)?			
Record any dose limiting toxicities (DLT's) on this form for any phase I investigator initiated trial, HOG or on a multi-site trial in which IUSCC is the lead site.			
If any of your answers are "NO" please explain in the space below.		•	
*Notes			

This form is to be used for Investigator Initiated and HOG trials (High risk weekly, Moderate risk Monthly, Low risk quarterly)

# A4.Appendix IV: Pain Scale

# Wong-Baker FACES® Pain Rating Scale

©1983 Wong-Baker FACES® Foundation. www.WongBakerFACES.org Wording modified for adult use. Used with permission.

# **A5.Appendix V: QOL Questionnaire**

See attached PDF "EORTC QLQ-30 (version 3)"
